1.1.2. Secondary Estimand(s)

The secondary efficacy estimand comprises the following 4 attributes:

- Population: Patients with achondroplasia, as defined by inclusion/exclusion criteria;
- Variable: Change from baseline to 24 months in the difference between arm span (cm) and standing height (cm);
- Intercurrent event: Withdrawal and all events leading to missing data will be excluded from efficacy analysis and will not have their data imputed;
- Population-level summary: Mean change-from-baseline of arm span/standing height difference at 24 months adjusted for age and gender.

1.2. Study Design

This is a Phase 2 open label extension study to assess the long-term safety, tolerability, PK and efficacy of recifercept.

Approximately 63 children from the Phase 2 C4181005 study will be offered to participate who, in the opinion of the investigator, continue to have a positive risk:benefit profile. Participants will be children diagnosed with achondroplasia aged $\geq 15\text{m}$ - ≤ 12 years (inclusive). All participants will continue to receive 1 of 3 doses of recifercept (1 mg/kg QW, 2 mg/kg BIW or 1.5 mg/kg QD) until a therapeutic dose is identified for up to 24 months.

Enrollment of participants will follow their completion of the C4181005 Phase 2 study and only be offered to those who, in the opinion of the investigator, continue to have a positive risk: benefit profile. PK and immunogenicity samples will be collected to assess long-term safety of recifercept.

Once a final therapeutic dose has been identified, the Pfizer IRC may decide to extend the study treatment duration and data collection (including final adult height) period beyond 24 months. Any significant changes to the protocol will be made via substantial protocol amendment.

2. ENDPOINTS AND BASELINE VARIABLES: DEFINITIONS AND CONVENTIONS

2.1. Primary Endpoint(s)

Safety

Safety and tolerability of recifercept as assessed through frequency and severity of AEs/SAEs.

Efficacy

Increase in height growth above expected in reference population [Merker et al, 2018].

2.2. Secondary Endpoint(s)

Safety

- Change from baseline in safety labs, vital signs, physical examination.
- Rate of anti-drug antibodies.

Efficacy

- Sitting height/standing height ratio.
- Arm span to height/length difference.
- Knee height:lower segment ratio.
- Occipito-frontal circumference.
- Ratio of occipito-frontal distance to occipito-mid-face measurements.
- z-score of the above proportionality and skull morphology where achondroplasia reference datasets exist (occipito-frontal circumference, arm span, sitting height).
- Fixed flexion angles at elbow.
- Polysomnography parameters in those with pre-existing sleep-disordered breathing at the time of enrollment.
- Body mass index (BMI).
- Waist:chest circumference ratio.

Pharmacokinetic

Population PK characterization in children aged >2 to <11 years old with achondroplasia. Clearance (CL/F) and other PK parameters of recifercept to assess exposures in different age group.

2.4. Baseline Variables

The following baseline variables will be summarized for each treatment group (per [Section 3](#)). Details of summary analyses are described in [Section 5.5.1](#).

Demographic characteristics:

- Baseline age
- Gender (female vs. male);
- Race (white, black, Asian, other);
- Baseline body weight;
- Baseline height (cm);
- Baseline Body Mass.

The baseline data measured at Day 1 are:

- Vital signs
- Physical Examinations

The following variables are to have their baseline value defined as latest screening result relative to Day 1:

- Medical history & demography, Height/Weight.
- Neurological Examinations
- Vital Signs/Physical Examinations with missing Day 1 values

Where Day 1 result is missing, baseline data will be defined as the latest result from C4181005 prior to enrollment, where available.

Medical history and concomitant medications ongoing from the C4181005 study will be reentered in C4181008 with the start date from when they entered into the C4181008 study.

2.5. Safety Endpoints

- laboratory data
- vital signs data
- physical examination

2.5.1. Adverse Events

Any events occurring following start of treatment or increasing in severity will be counted as treatment emergent.

Events that occur in a non-treatment period (for example, washout or follow-up) will be counted as treatment emergent and attributed to the previous treatment taken.

Any resolved AEs from study C4181005 will be reported as medical history. On-going AEs will be captured as ongoing with the start date from when they entered into the C4181008 study.

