### *Safety*

The safety data will be summarized in accordance with Pfizer Data Standards. All participants who receive IP (safety population) will be included in the safety analyses. All safety data will be summarized descriptively through appropriate data tabulations, descriptive statistics, categorical summaries, and graphical presentations. Safety endpoints for the study include:

- TEAEs and SAEs;
- Withdrawals from treatment due to AEs.

Change from baseline in laboratory data and vital signs will be additionally summarized. Participant listings will also be produced for these safety endpoints.

The primary efficacy estimand will be the population treatment effect of the mean change-from-baseline of a continuous response (ie, height, growth) at month 24 irrespective of IP compliance. Increase in height growth above expected growth in reference population, a co-primary endpoint, is defined as the height growth in the achondroplasia reference population +50%. Intercurrent event for the efficacy estimand: withdrawal and all events leading missing data will be excluded from efficacy analysis and will not have their data imputed. The population-based treatment effect will be the mean change-from-baseline at Month 24.

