4.1. Hypotheses and Decision Rules

There are no statistical hypotheses for this protocol.

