5.6. Safety Summaries and Analyses

All safety analyses will be performed on the safety population and summarized in accordance with Pfizer Data Standards.

All clinical AEs, SAEs, TEAEs, withdrawal due to AEs, ECGs, vital signs and safety laboratory data will be reviewed and summarized on an ongoing basis during the study to evaluate the safety of participants.

Safety data will be summarized descriptively through appropriate data tabulations, descriptive statistics, categorical summaries, and graphical presentations, where appropriate. Categorical outcomes (eg, AEs) will be summarized by subject counts and percentage. Continuous outcome (eg, blood pressure, pulse rate, etc.) will be summarized using N, mean, median, standard deviation, etc. Change from baseline (CFB) in laboratory data, and vital signs will also be summarized. Participant listings will be produced for the safety endpoints accordingly.

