5.6.1. Adverse Events

Adverse events will be reported in accordance with the sponsor reporting standards.

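### SAP 2.5.1 gives adverse events carried over from C4181005 the C4181008 entry date as onset, so records and listings show a false onset and old and new events cannot be cleanly separated

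*SAP*

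**What the plan says.** SAP 2.5.1 has three parts that matter here.

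- The treatment-emergent rule: "Any events occurring following start of treatment or increasing in severity will be counted as treatment emergent". It does not name the study whose treatment start is meant, and it has no rule for an event dated on the day of first dose.
- A second paragraph on non-treatment periods, with washout and follow-up as examples. Events in such a period count as treatment emergent and are attributed to the preceding treatment.
- The carry-over rule. Events that resolved in C4181005 become medical history. For the others, "On-going AEs will be captured as ongoing with the start date from when they entered into the C4181008 study".

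SAP 2.4 re-dates other carried-over data in the same way: "Medical history and concomitant medications ongoing from the C4181005 study will be reentered in C4181008 with the start date", that date again being entry into C4181008. The re-dating is therefore a deliberate convention.

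The primary safety endpoint is "Safety and tolerability of recifercept as assessed through frequency and severity of AEs/SAEs" (SAP 2.1). The Safety part of Protocol 9.3.2 lists "TEAEs and SAEs" among the safety endpoints and promises participant listings. SAP 5.6 names the categories separately: "All clinical AEs, SAEs, TEAEs, withdrawal due to AEs". SAP 5.6.1 adds only this: "Adverse events will be reported in accordance with the sponsor reporting standards".

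**The concern.** An extension study inherits events that began on drug in the parent study. A reader of the extension tables needs to know which events are new or worse and which were simply still there. The true onset date carries that information, and SAP 2.5.1 overwrites it.

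Two things are at stake. The first is the accuracy of the C4181008 record. Protocol 8.3.8 makes injection site reactions the event of special interest and asks for their onset and resolution dates. Protocol 6.8.3 asks for the duration of topical corticosteroid given for them. For a reaction that began in C4181005, both would start at the wrong date in C4181008, and a persistent reaction would look shorter than it was.

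The second is reproducibility. Two programmers working from SAP 2.5.1 could give different treatment-emergent counts from the same data.

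**Working it through.** The plan gives no figure to reproduce, so the check is of the date logic, followed by the weight of one child.

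**Do entry and first dose share a date?** The Schedule of Activities (Protocol 1.3) puts consent, dispensing and first administration in a single Enrollment column, and its footnote defines Day 1 as the start of study intervention. Protocol 1.1 ties enrollment to consent, and Protocol 8.3.1 starts adverse event collection at consent. A shared date is therefore likely. It is not certain: inclusion criterion 1, Protocol 8.2.5 and SAP 2.4 all refer to screening as something distinct from baseline or Day 1.

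**Date logic.** Take one unchanged event with invented dates: true onset 1 March 2022, first C4181008 dose (Day 1) 1 June 2022, still present on 30 June 2022. Apply only the first sentence of SAP 2.5.1, with treatment start taken as the first C4181008 dose.

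| Entry date | Onset used | On or after first dose? | Strictly after first dose? | Days to 30 June, inclusive |
|---|---|---|---|---|
| 1 June (Day 1) | true, 1 March | no | no | 122 |
| 1 June (Day 1) | per SAP, 1 June | **yes** | no | 30 |
| 29 May | true, 1 March | no | no | 122 |
| 29 May | per SAP, 29 May | no | no | 33 |

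With the true onset, the answer does not depend on the comparison or on the entry date; the event would count only if it worsened. With the assigned onset and same-day entry, the answer depends on a choice that the SAP does not make. The recorded duration is too short in both rows that use the assigned date.

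**Entry before first dose.** The last row is not settled by the first sentence alone. If the days between entry and first dose are a non-treatment period, the second paragraph of SAP 2.5.1 could make the event treatment emergent after all and attribute it to the earlier treatment.

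**If treatment start means the first C4181005 dose.** An event that began on recifercept in that study is treatment emergent with either date, and there is no miscount. SAP 2.5.1 does not exclude this reading.

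**Weight of one child.** The planned number is about 63 (Protocol 1.1). A child whose only treatment-emergent event is an unchanged carried-over one adds 1/63 = 0.0159, or 1.6 percentage points, to the overall percentage. If the 63 are split equally over three doses (an assumption), a group has 63/3 = 21 and the step is 1/21 = 4.8 points. If between 1 and 6 children were affected (an illustrative range, not from the documents), the overall excess would be 1.6 to 6/63 = 9.5 points. Under the strict comparison in the table it is 0.

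No total can be given. The only parent-study count is 16 adverse events in 6 children as of March 2021, 9 of them drug-related injection site reactions (Protocol 2.2.1), with no statement of how many were ongoing.

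**The case against.** A reader might infer that old events will be counted as new ones and that the treatment-emergent table is inflated. The documents do not support that. An on-or-after comparison is not the SAP's wording. Read literally, an event already present before dosing does not follow the start of treatment, and the separate limb for worsening suggests that unchanged events were not meant to count. The sponsor standards cited in SAP 5.6.1, or the CRF completion guidance cited in Protocol 10.1.7, may contain a same-day rule or a carry-over marker; neither is available here. This objection stands, and it makes the miscount a possibility only.

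A second stronger reading is that a planned analysis of onset or persistence is biased, or that the true dates are lost. That is not supported either. SAP 5.6 plans subject counts and percentages, with no analysis of adverse event duration or time to onset. Protocol 4.2.1 says the assessments match those of C4181005, so an injection site reaction that began there should have its onset recorded there. Protocol 8.3.8 and 6.8.3 do not expressly require parent-study dates to be recorded again.

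It is also fair to say that, where every child continues recifercept, counting an event that arose on drug in C4181005 as treatment emergent is a defensible convention. The SAP should then say so.

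None of this makes the assigned date correct. The false onset in the C4181008 record and listings follows from the carry-over rule under every reading of the treatment-emergent rule.

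**Conclusion.** The point holds and is minor. It is certain from the text that carried-over adverse events, and ongoing medical history and concomitant medications, receive a start date in C4181008 that is not their own. Listings, including those of injection site reactions, would then show a false onset and a shortened duration.

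It is conditional that an unchanged old event enters the treatment-emergent count. For same-day entry this needs two assumptions: that treatment start means the first C4181008 dose, and that same-day onsets are included. For earlier entry the text is unclear. Any such error can only overstate the count, and its size is unknown beyond the 1.6 points per affected child with no other treatment-emergent event.

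The effect on conclusions is limited, because the safety summaries are descriptive and SAP 4.1 states: "There are no statistical hypotheses for this protocol".

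**What to change.** - In SAP 2.5.1 and the CRF guidance, keep the original C4181005 onset date and event identifier in the C4181008 data and flag the event as carried over.
- In SAP 2.4, keep the original start date of ongoing concomitant medications.
- In SAP 2.5.1, state which study's first dose is the start of treatment, how an event dated on that day is classified, and how this fits with the paragraph on non-treatment periods. If a sponsor standard already settles this, cite it.
- Show unchanged carried-over events separately from events with onset or worsening after the first C4181008 dose. Either convention for the treatment-emergent label is then transparent.

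The cost is a few sentences of SAP and CRF-completion wording and a merge with C4181005 data that the sponsor holds. The reported treatment-emergent count may be lower as a result.

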2.5.2. Laboratory Data

Safety laboratory tests will be performed as described in the protocol.

To determine if there are any clinically significant laboratory abnormalities, the haematological, and blood chemistry safety tests will be assessed against the criteria specified in the sponsor reporting standards. The assessment will take into account whether each subject's baseline test result is within or outside the laboratory reference range for the particular laboratory parameter.

Baseline will be defined as the measurement on Day 1.

2.5.3. Physical Examination

Physical examination assessments will be performed as described in the protocol. Baseline will be defined as the last pre-dose measurement on Day 1.

3. ANALYSIS SETS (POPULATIONS FOR ANALYSIS)

Data for all participants will be assessed to determine if participants meet the criteria for inclusion in each analysis population prior to unblinding and releasing the database and classifications will be documented per standard operating procedures.

Population	Description
Full Analysis Set (FAS)/Safety	All participants receiving at least one dose of recifercept. Participants will be analyzed according to the dose they actually received.
Randomized (RAS)	All participants receiving at least one dose of recifercept. Participants will be analyzed according to the dose assigned from C4181005.
Per-Protocol Analysis Set (PPAS)	All participants receiving at least one dose of recifercept and have complete data at baseline through end of study or subject discontinuation and without protocol deviations that were thought to impact the efficacy evaluation during the treatment period. Participants will be analyzed according to the randomized intervention. Participants will be analyzed according to the dose assigned from C4181005.
PK Concentration set	All participants who received at least one dose of recifercept and have at least one evaluable concentration.

4. GENERAL METHODOLOGY AND CONVENTIONS

The final analysis will be performed after all study participants completed treatment and follow-up period, and the CSR will be issued after them.

4.1. Hypotheses and Decision Rules

There are no statistical hypotheses for this protocol.

4.2. General Methods

Data will be presented – ie, listed and summarized – by dose group, block and overall. Data summaries may also be grouped by gender. Continuous data will be summarized comprising mean, median, standard deviation, minimum and maximum. Categorical and binary data are summarized will be done via percentages.

4.2.1. Analyses for Longitudinal Continuous Endpoints

Mixed-effect, repeated measures (MMRM) models will be used. The fixed effects of treatment, visit, treatment-by-visit interaction, age and gender will be included. Visit will be modeled as a categorical covariate. (If the model does not converge then Visit will be modeled as a continuous covariate.) Unstructured covariance matrix will be assumed for the model errors. Compound symmetry covariance matrix will be used if the model with unstructured variance covariance doesn't converge.

When modeling the change from baseline values, the variable for visit will start with the first post-baseline visit. At each visit, estimates of least square mean (LSM) values and the LSM differences between treatment groups will be derived from the model. The corresponding p-values and 95% confidence intervals will also be derived from the model.

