### **Number of Participants**

Approximately 63 participants will be enrolled to study intervention.

Note: "Enrolled" means a participant's, or his or her legally authorized representative's, agreement to participate in a clinical study following completion of the informed consent process. A participant will be considered enrolled if the informed consent is not withdrawn prior to participating in any study activity.

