#### 4. STUDY DESIGN

##### 4.1. Overall Design

This is a Phase 2 open label extension study to assess the long-term safety, tolerability, PK and efficacy of recifercept.

Approximately 63 children from the Phase 2 C4181005 study will be offered to participate who, in the opinion of the investigator, continue to have a positive risk:benefit profile. Participants will be children diagnosed with achondroplasia aged  $\geq 15\text{m}$ - $\leq 12$  years (inclusive). All participants will continue to receive 1 of 3 doses of recifercept (1 mg/kg QW, 2 mg/kg BIW or 1.5 mg/kg QD) until a therapeutic dose is identified for up to 24 months.

Enrollment of participants will follow their completion of the C4181005 Phase 2 study and only be offered to those who, in the opinion of the investigator, continue to have a positive risk: benefit profile. PK and immunogenicity samples will be collected to assess long-term safety of recifercept.

Once a final therapeutic dose has been identified, the Pfizer IRC may decide to extend the study treatment duration and data collection (including final adult height) period beyond 24 months. Any significant changes to the protocol will be made via substantial protocol amendment.

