#### **4.3. Justification for Dose**

All participants will continue to receive 1 of 3 doses of recifercept (1 mg/kg QW, 2 mg/kg BIW or 1.5 mg/kg QD) as assigned in C4181005 study or at the therapeutic dose once this is identified. Dose will be adjusted according to weight every 3 months.

PK will be assessed on an ongoing basis using sparse sampling approach to inform and update the PopPK model.

Weight limits for this study ([Section 5.2](#)) are based on technical feasibility of dosing with the current study intervention formulation such that injection volumes will be between 0.2 mL and 1 mL.

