### 9.3.2. Primary Endpoint(s)/Estimand(s) Analysis

#### *Efficacy*

The primary efficacy endpoint of change from baseline of height at 24 months will be analyzed using an ANOVA model comprising terms for recifercept dose groups. Change from baseline estimates for height and their corresponding 95% confidence intervals will be provided via least-square means. The population for the primary analysis will be based on the FAS.

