5.2. Secondary Endpoint(s)

5.2.1. Arm span to height/length difference

5.2.1.1. Main Analysis

- Estimand strategy: Hypothetical ([Section 1.1.1](#)).
- Analysis set: FAS ([Section 3](#)).

- Analysis methodology: Change from baseline for Arm span to height/length difference will be analyzed MMRM including data from Months 3-24 with gender and whether a subject has switched doses of recifercept as covariates, subject (and/or time) as a random effect and an unstructured covariance matrix ([Section 4.2.1](#)).
- Intercurrent events and missing data: Data after study drug discontinuation and rescue will be excluded; intermediate missing values will not be imputed.
- The sample size, mean, standard deviation, median, minimum, and maximum at the baseline and postbaseline visits for observed standing height and change from baseline will be presented for each treatment arm.

The least-squares (LS) means, the 95% confidence interval for the LS means, the difference between the LS means for each pair of treatment groups, and the corresponding 95% confidence interval will be presented for change from baseline in standing height for all postbaseline visits.

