8. APPENDICES

Appendix 1. Summary of Efficacy Analyses

Endpoint	Analysis Type	Population	Data Inclusion and Rules for Handling Intercurrent Events and Missing Data	Analysis Model
Change from baseline to Month 24 in mean standing height	Summary	FAS	Separately for observed data and imputed data.	N/A
	Main analysis	FAS	All data collected will be included regardless of intercurrent events. Missing data will not be imputed.	MMRM with terms time,dose, gender & age
	Sensitivity/supplementary analysis	PPAS	All data collected will be included regardless of intercurrent events. Missing data will not be imputed.	MMRM with terms time,dose, gender & age
Change from baseline to Month 12 in mean arm span-height difference	Summary	FAS	Separately for observed data and imputed data.	N/A
	Main analysis	FAS	All data collected will be included regardless of intercurrent events. Missing data will be not be imputed.	MMRM with terms time,dose, gender & age
	Sensitivity/supplementary analysis	PPAS	All data collected will be included regardless of intercurrent events. Missing data will not be imputed.	MMRM with terms time,dose, gender & age

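### No height or arm-span model includes the baseline value of the outcome; this may cost precision in the dose comparisons, by an amount the documents do not settle

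*SAP*

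**What the plan says.** Seven places describe a model for height or for the arm span-height difference:

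- **Protocol 9.3.2, height:** Month 24 change "will be analyzed using an ANOVA model comprising terms for recifercept dose groups".
- **Protocol 9.3.3, arm span:** the same form, dose only.
- **SAP 4.2.1, general mixed model:** "The fixed effects of treatment, visit, treatment-by-visit interaction, age and gender will be included". Differences between treatment groups, with p-values and 95% intervals, are to be derived at each visit.
- **SAP 5.1.1.1, height growth:** gender, possibly age, and an indicator of dose switching. Pairwise dose differences with 95% intervals are to be shown at all visits after baseline.
- **SAP 5.2.1.1, arm span:** "with gender and whether a subject has switched doses of recifercept as covariates", with no age term.
- **SAP Appendix 1, both endpoints:** "MMRM with terms time,dose, gender & age".
- **SAP Appendix 4 code:** dose, month, gender and age. The response variable is named `height`.

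None of them has the baseline value of the outcome as a term.

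On numbers, the protocol synopsis says "Approximately 63 participants will be enrolled to study intervention". Protocol 4.1 says "All participants will continue to receive 1 of 3 doses of recifercept", and 4.3 adds "as assigned in C4181005 study or at the therapeutic dose once this is identified". For the full analysis set, SAP section 3 says "Participants will be analyzed according to the dose they actually received". No allocation ratio or per-dose sample size is given. SAP 4.1 states that there are no hypotheses.

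The primary variable (SAP 1.1.1, Appendix 2.2) is observed change in standing height divided by the change expected in the reference population for age and gender. SAP 1.1.1 takes its baseline from C4181005 without naming the visit. SAP 2.4 defines baseline height as the latest screening result relative to Day 1.

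**The concern.** Both modelled endpoints are built on a change from baseline. Error in the baseline measurement enters every later change with a negative sign, so baseline and change can be correlated even without a biological link. Where they are correlated given the other model terms, leaving baseline out has two effects:

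- residual variance that could have been explained stays in the dose contrasts;
- a dose group that starts shorter for age, or with a larger arm-span deficit, carries part of that difference into its estimated change.

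The groups are small, and they consist of children who completed C4181005 and were judged suitable to continue. Doses may also be reduced for tolerability (protocol 6.5) or moved to the therapeutic dose. Close baseline balance between doses therefore cannot be taken for granted. With no hypothesis test planned, the width and centring of the intervals are what the dose comparison delivers.

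**Working it through.** The documents give no standard deviation, correlation, power or precision target, so there is no stated figure to reproduce. The calculation below treats one visit as a simple comparison of two doses, in units of the SD of change.

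**1. Group size.** 63 / 3 = 21 per dose, assuming equal allocation, full rollover and no switching.

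**2. Half-width without baseline.** t(0.975; 60 df) × sqrt(2/21) = 2.000 × 0.3086 = 0.617 SD. With the normal quantile it is 0.605 SD. At 15 or 10 per dose the normal version is 0.72 or 0.88 SD.

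**3. Adding baseline.** Let r be the correlation of baseline with change, given the terms already in the model. The half-width is multiplied by sqrt(1 - r²). One covariate costs a factor sqrt(1 + 1/58) × t(59 df)/t(60 df) = 1.0086 × 1.0003 = 1.0089. The values of r are assumed.

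| r | sqrt(1 - r²) | net factor | half-width (SD) | net change |
|---|---|---|---|---|
| 0 | 1.000 | 1.0089 | 0.623 | +0.9% |
| 0.1 | 0.995 | 1.0039 | 0.620 | +0.4% |
| 0.2 | 0.980 | 0.9886 | 0.610 | -1.1% |
| 0.3 | 0.954 | 0.9625 | 0.594 | -3.8% |
| 0.5 | 0.866 | 0.8738 | 0.539 | -12.6% |

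Break-even is at r = sqrt(1 - 1/1.0089²), about 0.13.

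**4. The same in terms of tracking.** If baseline and Month 24 have equal variance and correlation rho, then 1 - r² = (1 + rho)/2. For assumed rho of 0.5, 0.8, 0.9, 0.95 and 0.98, the half-width falls by 13.4%, 5.1%, 2.5%, 1.3% and 0.5% before the 0.9% covariate cost. The last of these is a small net loss.

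**5. Imbalance.** With 21 per dose, the chance difference in mean baseline between two doses has standard error sqrt(2/21) = 0.31 baseline SD. One standard error of imbalance moves the unadjusted dose difference by r × 0.31, which is 0.03, 0.06, 0.09 or 0.15 SD of change for r = 0.1, 0.2, 0.3 or 0.5.

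**6. Does age already do the work?** An illustrative simulation used assumed growth values: 63 children aged 1.25 to 12 years, with two-year change falling by 0.4 cm per year of age. The standard error (cm) of a pairwise dose difference was:

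| r given age | dose only | + age | + age and baseline |
|---|---|---|---|
| 0 | 0.60 | 0.46 | 0.47 |
| 0.3 | 0.59 | 0.47 | 0.45 |
| 0.5 | 0.60 | 0.47 | 0.41 |

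Age gives most of the gain here. Baseline adds to it only when it predicts change beyond age.

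**The case against.** Several parts of the opposing case stand.

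- **The loss is not demonstrated.** It depends on a correlation the documents do not give. A reader might infer that precision is certainly lost, for instance by quoting only r = 0.3 to 0.5 and an equivalent sample of 63/(1 - r²) = 69 to 84 children. That is the favourable end of the range; below about 0.13 the covariate costs slightly more than it returns.
- **Height is already standardised.** The ratio divides by expected growth for age and gender, and age and gender are also in SAP 4.2.1, Appendix 1 and the Appendix 4 code. Over an age range of 15 months to 12 years, age may carry much of the information in baseline height. The denominator does not, however, use a child's own deviation from the reference mean. Arm span has no such standardisation in the modelled change.
- **Imbalance is not kept whole.** A reader might infer that baseline differences pass straight into the dose contrasts. Subtracting baseline removes the difference in level; only the part that predicts change remains. Protocol 2.2.1 also describes C4181005 participants as randomised to dose. Rollover and switching may disturb that balance, but the documents do not show how far.
- **Baseline adjustment can do harm.** The schedule of activities shows no anthropometry at enrolment. A value from extension entry or the end of C4181005 would have been measured on treatment, and adjusting for it could remove part of the dose effect.
- **The stakes are limited.** There are no hypotheses, and the primary efficacy contrast is with a reference population, not between doses. Omitting baseline is an efficiency choice, not an invalid analysis.

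These points limit the size of the concern and set conditions on the fix. They do not answer the omission itself: dose differences with intervals are planned, and a value every change score already needs is left out of all seven model descriptions.

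**Conclusion.** The omission is established: no height or arm-span model adjusts for the baseline value of the outcome. Its consequence is possible, not proven. The dose contrasts may be less precise than they could be, and they retain the part of any baseline imbalance that predicts change.

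Net of the covariate cost, the effect on interval half-width runs from about +0.9% at r = 0, through -3.8% at r = 0.3, to -12.6% at r = 0.5. These figures assume 21 children per dose and a single-visit comparison, and r is not in the documents. The gain may be small for the age- and gender-standardised height ratio. The case is strongest for arm span under SAP 5.2.1.1, where age is missing too; the dose-only protocol models share that gap. The documents do not support reading this as a demonstrated loss of a given size, or as a bias known to be present.

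Adding baseline is still worthwhile. The downside is an interval about 1% wider if baseline proves uninformative.

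**What to change.** 1. **Settle baseline first.** Reconcile SAP 1.1.1 with 2.4 by naming one pre-treatment C4181005 record. Use that same record for the change score and the covariate, and start the expected change in the denominator from it.
2. **Add the covariate.** Put baseline, together with age and gender, into the mixed models in SAP 4.2.1, 5.1.1.1 and 5.2.1.1, Appendix 1 and the Appendix 4 code. For the growth ratio, use baseline height minus the reference mean for age and sex. For arm span, use the baseline arm span-height difference. Align protocol 9.3.2 and 9.3.3.
3. **Make baseline-by-visit conditional.** Anthropometry is scheduled at eight visits (Months 3 to 24). A separate baseline slope at each visit means up to eight parameters in place of one, alongside an unstructured covariance in about 63 children. Include it only if the model supports it.
4. **Do not adjust for an on-treatment value** taken at extension entry.

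The cost is SAP wording and code, with a protocol change if the sponsor regards this as a major modification of the primary analysis. No new data are needed if the pre-treatment C4181005 measurements are available, as a change score from that baseline already requires.
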